5. AMENDMENTS AND UPDATES

Version Identifie r	Date	Amendment Type (substantial or administrative	Protocol section(s) changed	Summary of amendment(s)	Reason
2	January 2021	Substantial	Pass information table	Updated to reflect changes in study title and objectives. Addition of EU PAS registration number and updates to protocol date, version, and product reference number.	Amendment of protocol to include drug utilization study component
		Substantial	Section 1	Table of contents updated to include additional sections for drug utilization study component added to protocol, and additional section to define index date for drug utilization and active surveillance components	Amendment of protocol to include drug utilization study component
		Administrative	Section 2	List of abbreviations updated to include new abbreviations, and to update definition for VTE from venous thromboembolic events to venous thromboembolism	Editorial changes
		Substantial	Section 4	Significant and editorial changes to abstract to reflect addition of drug utilization component to study protocol, including updates to study title to reflect both drug utilization and active surveillance components, updates to rationale and background, research questions and objectives, study design,	Amendment of protocol to include drug utilization study component

Version Identifie r	Date	Amendment Type (substantial or administrative	Protocol section(s) changed	Summary of amendment(s)	Reason
				population, variables, study size, data analysis and milestones.	
		Administrative	Section 6	Update to study milestones to reflect start date of drug utilization component of study, and change to date of final report submission to within 12 months of the end of data collection	Amendment of protocol to include drug utilization study component
		Substantial	Section 7	Updates to rationale and background to provide more information on approved indications/dose in the US and changes to overall goal of study to include drug utilization component Specification that study is not only a commitment to US FDA, but also a category 3 study in the European Union risk management plan	Amendment of protocol to include drug utilization study component
		Substantial	Section 8	Updated to include research questions and objectives for drug utilization component	Amendment of protocol to include drug utilization study component
		Substantial	Section 9.1	Updated study design information to include new study observation period (from November 2012 (time of first of US approval for tofacitinib) through to June 2025); updates to study description to include analysis to	Amendment of protocol to include drug utilization study component

Version Identifie r	Date	Amendment Type (substantial or administrative	Protocol section(s) changed	Summary of amendment(s)	Reason
				assess tofacitinib utilization patterns	
		Substantial	Section 9.2.1	Updated to specify inclusion criteria for drug utilization component Clarifications and editorial changes to inclusion criteria for active surveillance component	Amendment of protocol to include drug utilization study component Editorial changes
		Substantial	Section 9.2.2	Updated to specify that no exclusion criteria will be applied for the drug utilization component	Amendment of protocol to include drug utilization study component
		Administrative	Section 9.3	Editorial changes	Editorial changes
		Substantial	Section 9.3.1	Clarification to specify baseline variables for both drug utilization and active surveillance components Addition of history of heart failure, prior TNFi use and use of oral contraceptives/hormona l therapy as baseline variables	Amendment of protocol to include drug utilization study component Clarifications/editoria l changes
		Substantial	Section 9.3.1.1	New sub-section to define thrombosis risk factors	Amendment of protocol to include drug utilization study component
		Substantial	Section 9.3.2	New sub-section to define on-label and off- label use for drug	Amendment of protocol to include drug utilization study component

Version Identifie r	Date	Amendment Type (substantial or administrative	Protocol section(s) changed	Summary of amendment(s)	Reason
				utilization component of study	
		Substantial	Section 9.3.3	New sub-section to define prescribed daily dose and duration of tofacitinib therapy for drug utilization component of study	Amendment of protocol to include drug utilization study component
		Substantial	Section 9.3.4	New section to define index dates for drug utilization component (Section 9.3.4.1) and active surveillance component (Section 9.3.4.2)	Amendment of protocol to include drug utilization study component Clarification of index date
		Substantial	Section 9.3.5	Updated to include illustration for astreated approach with the 90-day extension period, and to specify additional sensitivity analysis to be conducted for this approach	Clarification of follow-up in active surveillance component Editorial changes
				Editorial change to section title	
		Substantial	Section 9.3.6	Updated to include endpoint of interest for drug utilization component of study	Amendment of protocol to include drug utilization study component
				Editorial changes to safety outcomes of interest for active surveillance component	Editorial changes
		Substantial	Section 9.5	Updated study size to provide preliminary data on number of patients with ≥ 1 tofacitinib prescription in data source	Amendment of protocol to include drug utilization study component

Version Identifie r	Date	Amendment Type (substantial or administrative	Protocol section(s) changed	Summary of amendment(s)	Reason
		Administrative	Section 9.7	Editorial changes	Editorial changes
		Substantial	Section 9.7.1	New sub-section to provide overview of analysis plan for drug utilization component of study	Amendment of protocol to include drug utilization study component
		Substantial	Section 9.7.2	Updated to specify subgroup analyses for active surveillance component	Clarifications to specify subgroup analyses for active surveillance component
		Substantial	Section 9.7.3	Updated to note that interim data from drug utilization component of study will be included	Amendment of protocol to include drug utilization study component
				Editorial changes	Editorial changes
		Substantial	Section 9.7.4	Updated to note that final data from drug utilization component of study will be included	Amendment of protocol to include drug utilization study component
				Editorial changes	Editorial changes
		Administrative	Section 9.9	Editorial changes to reflect amendment of protocol to include drug utilization study component	Editorial changes to reflect amendment of protocol to include drug utilization study component
		Administrative	Section 12	Editorial changes	Editorial changes
		Substantial	Section 14	Updated to include new table	Editorial change
		Administrative	Annex 2	Signature date for Encepp checklist	Editorial change

Version Identifie r	Date	Amendment Type (substantial or administrative	Protocol section(s) changed	Summary of amendment(s)	Reason
3	30 September 2024	Administrative	Title page	Editorial changes to section title	Editorial changes
		Substantial	Title page	Updated to include additional safety events of interest Updated to reflect stratification in subgroup analyses	Amendment of protocol to include additional safety events of interest Amendment of protocol to reflect individual dosing analyses
		Administrative	Section 2	List of abbreviations updated to include new abbreviations for HMA and RWD	Editorial changes
		Administrative	Section 3	Editorial changes to responsible parties	Editorial changes
		Administrative	Section 4	Editorial changes to abstract	Editorial changes
		Substantial	Section 4	Updated to include additional safety events of interest	Amendment of protocol to include additional safety events of interest
		Administrative	Section 6	Editorial changes to milestones	Editorial changes
		Substantial	Section 8	Updated to include additional safety events of interest Updated to reflect stratification in subgroup analyses	Amendment of protocol to include additional safety events of interest Amendment of protocol to reflect individual dosing analyses
		Administrative	Section 9.2.1.	Editorial changes	Editorial changes

Version Identifie r	Date	Amendment Type (substantial or administrative	Protocol section(s) changed	Summary of amendment(s)	Reason
		Substantial	Section 9.3.6.	Updated to include additional safety events of interest	Amendment of protocol to include additional safety events of interest
		Substantial	Section 9.7.2	Updated to reflect stratification in subgroup analyses	Amendment of protocol to reflect individual dosing analyses
		Substantial	Section 9.7.4	Updated to reflect stratification in subgroup analyses	Amendment of protocol to reflect individual dosing analyses

6. MILESTONES

Milestone	Planned date
Start of data collection	30 June 2020*
End of data collection	30 June 2025
Interim report 1	30 June 2022
Interim report 2	30 June 2024
Registration in the HMA-EMA Catalogues of RWD Studies	Prior to start of data collection
Final study report	30 June 2026

^{*}This represents the start of data collection for the active surveillance portion of the study. Start of data collection for the drug utilization study will be 31 March 2021.

7. RATIONALE AND BACKGROUND

Ulcerative colitis (UC) is a type of inflammatory bowel disease (IBD) characterized by chronic inflammation of the gastrointestinal tract, marked by an abnormal immune response. UC is restricted to the colon and affects the mucosa of the gut¹. As a result of the inflammatory reaction, the intestinal wall is damaged, frequently leading to bloody diarrhea and abdominal pain.

UC presents significant health and socioeconomic burdens for the individual patient and society^{6,7,8}. There is currently no cure for UC¹. Moderate-to-severe UC often requires treatment with systemic agents, such as glucocorticoids and azathioprine⁹, many of which are associated with infectious, cardiovascular, gastrointestinal and malignant adverse events^{10,11}. Tofacitinib, an inhibitor of the Janus kinase (JAK) family of kinases, was approved in the United States (US) in May 2018 at a dose of 5 mg twice daily or 10 mg twice daily for the treatment of adults with moderate-to-severe UC. In July 2019, the US prescribing information (USPI) was updated to note that tofacitinib should be prescribed for adult patients with moderate-to-severe UC who have had an inadequate response or who are intolerant to tumor necrosis factor inhibitors (TNFis). In December 2019, the extended-release formulation was also approved for UC patients at a dose of 11 mg once daily and 22 mg once daily. Use of tofacitinib in combination with biological therapies for UC or with potent immunosuppressants such as azathioprine and cyclosporine is not recommended.

Tofacitinib is also currently approved for three other indications in the US, and these include in adults with moderate-to-severe rheumatoid arthritis (RA) who have had an inadequate response or intolerance to methotrexate (MTX), in adults with active psoriatic arthritis who have had an inadequate response or intolerance to MTX or other disease-modifying antirheumatic drugs (DMARDs), and in patients ≥2 years with active polyarticular course

juvenile idiopathic arthritis (pcJIA). For RA, PsA and pcJIA patients, use of tofacitinib in combination with biologic DMARDs or potent immunosuppressants such as azathioprine and cyclosporine is not recommended. Additionally, for RA and PsA patients, only the 5 mg twice daily and 11 mg once daily dosing regimens are approved; the 10 mg twice daily and 22 mg once daily dosing regimens are not indicated for use in non-UC patients. For pcJIA patients, only the 5 mg twice daily dosing regimen is approved. Due to the potential for off-label use of the 10 mg twice daily and 22 mg once daily dosing regimens in non-UC patients, as well as the potential for use of tofacitinib in non-indicated populations, it would be useful to understand the patterns of post-approval use in the US.

In addition, understanding of long-term safety associated with real-world tofacitinib use, including the potential risk of malignancy and other safety events of interest, is needed. Follow up of large cohorts of patients over a long period can help in the evaluation of any potential risk of malignancy, as well as other potential safety events of interest that may be associated with tofacitinib treatment. It is important that surveillance also examines patient co-morbidities which may influence the occurrence of safety events, as well as mortality. Active surveillance studies help assess the risk of safety events of interest overall and within strata of disease severity, treatment history, patient co-morbidities or risk factors and other concomitant therapy.

To understand the patterns of tofacitinib use in the US, as well as to characterize the risk of safety events of interest that may be associated with its use, a non-interventional, drug utilization and active surveillance study will be conducted using data from the International Business Machines (IBM) Watson Health MarketScan® Research Databases. This non-interventional study is designated as a Post-Authorization Safety Study (PASS) and is a post-marketing commitment to the US Food and Drug Administration (FDA). It is also a category 3 study in the tofacitinib European Union (EU) risk management plan (RMP).

8. RESEARCH QUESTIONS AND OBJECTIVES

The research questions and associated objectives for this study are as follows:

Research Question 1:

What are the utilization patterns of tofacitinib in the US with regard to on-label and off-label use?

Objectives:

- Estimate the proportion of tofacitinib users who receive the drug for the approved indications during the study period
- Describe the characteristics of patients who are prescribed to facitinib for on-label, off-label and unknown indications in terms of the following:
 - Demographics (e.g., age, sex);

- Comorbidities;
- Prior and concurrent medications;
- Prescribed daily dose and duration of tofacitinib therapy
- Estimate the proportion of UC patients on 5 mg twice daily or 11 mg once daily and 10 mg twice daily or 22 mg once daily maintenance therapies
- Estimate the proportion of non-UC patients on 10 mg twice daily or 22 mg once daily therapy
- Estimate the proportion of patients with approved indications who have ≥1 thrombosis risk factors and are prescribed tofacitinib, overall and stratified by dose
- Estimate the proportion of TNFi-naïve UC patients prescribed tofacitinib pre and post 01 July 2019

Research Question 2:

What are the incidence rates of safety events of interest in adult ulcerative colitis (UC) patients treated with tofacitinib (including the immediate-release formulation [dosed as 5 mg and 10 mg twice daily] and the extended-release formulation [dosed as 11 mg and 22 mg once daily] formulations) in the course of routine clinical care?

Primary Objective:

The primary objective is to estimate the incidence rate of malignancy, excluding non-melanoma skin cancer (NMSC), among adult UC patients who initiate tofacitinib in the course of routine clinical care.

Secondary Objective:

The secondary objective is to estimate the incidence rates of other safety events of interest among adult UC patients who initiate tofacitinib in the course of routine clinical care. These other safety events include (but may not be limited to) the following:

- Lung cancer
- Lymphoma
- NMSC
- Serious infections
- Opportunistic infections (e.g. tuberculosis)
- Herpes zoster (HZ) reactivation
- Major adverse cardiac events (MACE)
- Venous thromboembolism (VTE; deep venous thrombosis [DVT] and pulmonary embolism [PE])
- Myocardial Infarction (MI)
- Hepatic events

- Progressive multifocal leukoencephalopathy (PML)
- Gastrointestinal (GI) perforations
- Interstitial lung disease (ILD)
- Fractures
- Surgery for UC
- Death

For contextualization and risk characterization purposes, the incidence rates of the same safety events (listed in the primary and secondary objectives above) in adult UC patients initiating treatment with other approved systemic agents, as well as those patients naïve to biologics and immunomodulators/immunosuppressants will also be assessed. Therefore in total, incidence rates will be estimated within the following groups:

1. Cohort 1 (Tofacitinib cohort): UC patients initiating tofacitinib, overall and independently stratified by dose (5 mg twice daily, 11 mg once daily, 10 mg twice daily, 22 mg once daily) and prior biologic use (i.e. patients naïve to biologics vs. patients with prior biologic use)

Contextualization Cohorts:

- 2. Cohort 2 (Biologics cohort): UC patients who initiate biologics, with/without concurrent immunomodulators/immunosuppressants, overall and independently stratified by TNFi/non-TNFi use and number of previous biologic treatments
- 3. Cohort 3 (Immunomodulators/immunosuppressants cohort): UC patients who initiate immunomodulators/immunosuppressants (methotrexate [MTX], azathioprine [AZA], mercaptopurine [6-MP]) without concurrent biologics
- 4. Cohort 4 (Naïve cohort): UC patients naïve to both biologics and immunomodulators/immunosuppressants

Patients in the naïve cohort are expected to have milder disease relative to patients in the other 3 cohorts.

9. RESEARCH METHODS

9.1. Study Design

This is a descriptive, drug utilization and active surveillance, secondary data collection study of patients with ≥ 1 to facitinib prescription in the IBM Watson Health MarketScan® Research Databases from November 2012 (time of first of US approval for to facitinib) through to 30 June 2025.

To assess tofacitinib utilization patterns, the proportion of tofacitinib users who receive the drug for the approved indications during the study period will be estimated, and the demographic and clinical characteristics patients who are prescribed tofacitinib for on-label, off-label, and unknown indications will also be described. Among patients with on-label (approved) indications (i.e. RA, PsA, UC, pcJIA), the proportion of tofacitinib prescriptions

with off-label dosing, stratified by approved indication, will be estimated. Additionally, the proportions of UC patients on 5 mg twice daily/11 mg once daily and 10 mg twice daily/22 mg once daily maintenance therapies, non-UC patients on 10 mg twice daily/22 mg once daily therapy and patients with approved indications who have ≥1 thrombosis risk factors and are prescribed tofacitinib (overall and stratified by dose), as well as the proportion of TNFinaïve UC patients prescribed tofacitinib pre and post 01 July 2019 will be described. To characterize the risk of the various safety events of interest, incidence rates and associated 95% confidence intervals (CIs) will be calculated in the four cohorts described in Section 8. No a priori hypotheses are specified.

9.2. Setting

The IBM Watson Health MarketScan® Research Databases is a US administrative healthcare database containing 143 million unique patients since 1996. It is a nationally representative data sample of Americans with employer-provided health insurance, as well as Medicare, and contains complete information on outpatient prescriptions and both inpatient and outpatient diagnoses.

9.2.1. Inclusion Criteria

Patients must meet all of the following inclusion criteria to be eligible for inclusion in the study.

9.2.1.1. Drug Utilization Study

To assess utilization patterns of tofacitinib use, all patients enrolled in the Marketscan database during the study observation period (i.e. from time of first US approval for tofacitinib in 2012 through to end of data collection in 2025) who have received ≥ 1 prescription of tofacitinib will be included.

9.2.1.2. Active surveillance study

The active surveillance population to be used for the estimation of the incidence rates of the safety events of interest will be a subset of the population described above, and will include all adult UC patients aged ≥18 years who are enrolled in the Marketscan database from the time of approval of tofacitinib for UC in the US (May 2018) through to the end of data collection (June 2025) for the study. UC patients will be identified via ICD-10 codes listed in Table 1. Using all available data, UC patients must have at least one UC diagnosis code from an inpatient visit, or at least two occurrences of a UC diagnosis code from outpatient vists, with at least one of the two outpatient codes documented by a gastrointestinal specialist. UC codes assigned on different dates do not need to be the same to qualify. At least 12 months of continuous (i.e., no more than a 30-day gap) database enrollment before index date is required to enable analysis of baseline patient and disease characteristics that may be important modifiers of the relationship of UC with safety endpoints of interest. Index date is defined in the treatment cohort inclusion criteria listed in the subsections below.

ICD-9 Code	Diagnosis	ICD-10 code	Diagnosis
556 (no 3 rd digit)	Ulcerative colitis		
556.0	Ulcerative enterocolitis	K51.8 (all billable codes under K51.8)	Other UC
556.1	Ulcerative ileocolitis	K51.8 (all billable codes under K51.8)	Other UC
556.2	Ulcerative proctitis	K51.2 (all billable codes under K51.2)	Ulcerative (Chronic) Proctitis
556.3	Ulcerative proctosigmoiditis	K51.3 (all billable codes under K51.3)	Ulcerative (Chronic) Rectosigmoiditis
556.5	Left-sided ulcerative colitis	K51.5 (all billable codes under K51.5)	Left Sided Colitis
556.6	556.6 Universal ulcerative colitis		Ulcerative (Chronic) Pancolitis
556.8	Other ulcerative colitis	K51.8 (all billable codes under K51.8)	Other Ulcerative Colitis
556.9	Ulcerative colitis, unspecified	K51.9 (all billable codes under K51.9)	Ulcerative Colitis, Unspecified

Table 1. ICD Codes for UC Diagnoses within MarketScan Database

Patients may switch between the tofacitinib and contextualization cohorts over time if inclusion/exclusion criteria listed below are met. Additionally, patients will be eligible for entry into a particular cohort each time they start a new therapy within the same drug class. For acute endpoints, patients will be censored from a particular cohort when they start a new therapy in a different drug class. For the endpoint of MACE, for example, patients in Cohort 1 (UC patients initiating treatment with tofacitinib) will be censored if and when they switch to a specific biologic agent, but will be eligible for subsequent inclusion into Cohort 2 (patients initiating treatment with biologics). For non-acute outcomes such as malignancy and death, outcomes will be evaluated using a "once exposed always at risk" paradigm (as described in Section 9.3.5).

Formal definitions of index dates/start of follow-up are provided in Sections 9.3.4.2 and 9.3.5.Details of exposure measurement (e.g., allowing specified gaps between prescriptions in continuous exposure, etc.) will be detailed in the statistical analysis plan (SAP).

9.2.1.2.1. Cohort 1 (Tofacitinib cohort): Adult UC Patients Treated with Tofacitinib

1. Initiation of tofacitinib as captured in Marketscan since 30 May 2018 (i.e. first tofacitinib prescription occurring either after the first UC diagnosis code from an inpatient visit or after the second UC diagnosis code from an outpatient visit and following US approval of tofacitinib for UC).

Note that in the US, as per the US prescribing information (USPI), tofacitinib is not expected to be prescribed to newly diagnosed UC patients, and since UC is a chronic condition, it is expected that the majority of UC patients receiving tofacitinib would have previously been prescribed other forms of UC therapy. For those patients with

an outpatient diagnosis of UC, it is unlikely that many, if any at all, will receive a prescription for tofacitinib after the first UC diagnosis code (and before the second UC diagnosis code).

2. Patients with either 1 UC diagnosis code from an inpatient visit or ≥2 of any of the ICD-10 codes for UC in Table 1 from an outpatient visit prior to the index date (i.e. date of first prescription of tofacitinib) (at least one of the two required UC diagnoses from outpatient visits must be made by a gastrointestinal specialist.

As per recommendations from the USPI, patients in this cohort may not be on potent immunomodulators/immunosuppressants concurrently.

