9.2.2. Exclusion Criteria

To assess to facitinib utilization patterns, no exclusion criteria will be applied. However, for the active surveillance population which will consist of a subset of the study population, patients not meeting the inclusion criteria for any of the respective cohorts described above will be excluded.

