9.3.1. Baseline Data

Baseline data for both the drug utilization and active surveillance components of the study will include the following, as appropriate:

- Age (years) at index date
- Sex (male/female)
- Age of UC onset (years)/years since UC diagnosis (i.e. from date of first inpatient UC diagnosis code or second outpatient UC diagnosis code to index date)
- Smoking status (yes/no as per algorithm based on diagnosis and procedure codes²⁴)
- Comorbidities (within 12 months of index date for non-malignancy events, and ever for malignancy events) e.g.
 - o history of malignancies,
 - o history of serious infection,
 - o history of opportunistic infection,
 - o history of herpes zoster,
 - history of venous thromboembolism,
 - history diabetes mellitus,
 - o history of myocardial infarction [MI],
 - history of heart failure

- o history of hypertension,
- history of inherited coagulation disorders
- Prior TNFi use (using all available data)
- Concomitant use of immunomodulators/immunosuppressants at index date
- Use of the following medications within 12 months of index date:
 - o oral contraceptives or hormonal therapy
 - o oral steroids,
 - o oral nonsteroidal anti-inflammatory drugs [NSAIDs],
 - o antimicrobials,
 - o anticoagulants,
 - o beta blockers,
 - o bisphosphonates,
 - o narcotics,
 - proton pump inhibitors [PPIs]
 - statins

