- 2. Between February 2016 and November 2017, a prescription of tofacitinib 11 mg once daily occurring only after a diagnosis of RA (as defined above)
- 3. After December 2017, a prescription of tofacitinib 5 mg twice daily or 11 mg once daily occurring only after a diagnosis of either RA or PsA (as defined above)
- 4. After May 2018, a prescription of tofacitinib 5 mg twice daily occurring only after a diagnosis of either RA, PsA or UC (as defined above)
- 5. After May 2018, a prescription of tofacitinib 10 mg twice daily occurring only after a diagnosis of UC (as defined above)
- 6. After December 2019, a prescription of tofacitinib 11 mg once daily or 22 mg once daily occurring only after a diagnosis of UC (as defined above)
- 7. After September 2020, a prescription of tofacitinib 5 mg twice daily occurring only after a diagnosis of RA, PsA, UC or pcJIA.

For each approved indication of tofacitinib (i.e. RA, PsA, UC, pcJIA), the proportion of tofacitinib prescriptions with off-label dosing will be estimated as described in Section 9.7.1.

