9.7.2. Analysis of safety endpoints of interest

For the safety endpoints of interest, descriptive statistics, counts and proportions, cumulative incidence proportions, and crude incidence rates (i.e., number of events per person-years) and associated two-sided 95% confidence intervals will be calculated as appropriate. UC patients with a baseline history of an outcome of interest will be excluded from the calculation of the incidence rate for that particular outcome of interest (e.g. patients with a baseline history of malignancy will be excluded from the calculation of the incidence rate for malignancy).

Several subgroup analyses will be performed. These include (but are not limited to) stratification by:

- Tofacitinib dose (5 mg twice daily vs. 11 mg once daily vs. 10 mg twice daily vs. 22 mg once daily)
- Patient characteristics such as age at index date, including a subgroup analysis of patients <50 years vs. ≥50 years, and patients <65 years vs. ≥65 years
- For the outcomes of VTE and MACE, subgroup analysis of patients with ≥1 thrombosis risk factors (as defined in Section 9.3.1.1) vs. no thrombosis risk factors, and
- Key indicators of disease severity such as number of previous biologic treatments (i.e. prior biologic use vs. none; among those with prior biologic use, 1st biologic vs. 2nd biologic vs. ≥3 biologics)

This will be a time to first event analysis based on an index date defined for each cohort with appropriate censoring rules applied (based on therapy switches, end of study, etc.) for those

who do not experience an event by end of follow-up period. Rates will be expressed as the number of events/100 person-years of follow-up.

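### Cohort 1 does not tie the tofacitinib prescription to UC, so the crude dose-stratified safety rates may be confounded by coexisting RA or PsA; size and direction cannot be told from the protocol

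*Protocol*

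**What the plan says.** Entry to Cohort 1 rests on diagnosis codes and a prescription (Protocol 9.2.1.2.1). The patient needs "Patients with either 1 UC diagnosis code from an inpatient visit or ≥2 of any of the ICD-10 codes for UC in Table 1" before the index date, with one of the outpatient codes coming from a gastrointestinal specialist. Concurrent potent immunosuppressants are not allowed. Section 9.2.2 adds only that "patients not meeting the inclusion criteria for any of the respective cohorts described above will be excluded".

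On dose, Section 7 states that "for RA and PsA patients, only the 5 mg twice daily and 11 mg once daily dosing regimens are approved". Table 2 in 9.3.2 gives the approval dates by indication and formulation.

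On analysis, 9.7.2 says "crude incidence rates (i.e., number of events per person-years) and associated two-sided 95% confidence intervals will be calculated", with one subgroup split defined as "Tofacitinib dose (5 mg twice daily vs. 11 mg once daily vs. 10 mg twice daily vs. 22 mg once daily". Section 9.7.4 repeats that split for the final report. RA and PsA are not among the named baseline comorbidities in 9.3.1, an open list introduced as "Comorbidities (within 12 months of index date for non-malignancy events, and ever for malignancy events) e.g". They are not among the named subgroups in 9.7.2 either, which is also an open list.

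**The concern.** Research Question 2 asks for event rates in UC patients, and the final report sets those rates side by side for four regimens. If some patients in the lower-dose strata received tofacitinib for arthritis, those strata differ from the higher-dose strata by indication as well as by dose. The rates are crude, so nothing in the stated analysis would remove or even show the difference. A reader who compares the 11 mg or 5 mg rate with the 10 mg or 22 mg rate could then take an effect of case mix for an effect of dose, or miss a dose gradient.

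The protocol already has the means to see this. Section 9.3.2 defines RA and PsA from claims and classifies the indication of every tofacitinib user, but that classification is used only in the utilization part and is not carried into the safety cohorts.

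**Working it through.** **Step 1: can such patients enter?** Yes. The inclusion criteria in 9.2.1.2 and 9.2.1.2.1 look at UC codes and timing only, and 9.2.2 has no further exclusion. A patient with qualifying UC codes and an RA or PsA diagnosis enters whichever condition prompted the prescription.

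**Step 2: is there reason to expect them in particular dose strata?** The dates in Table 2 are:

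| Regimen | RA | PsA | UC |
|---|---|---|---|
| 5 mg twice daily | 6 Nov 2012 | 14 Dec 2017 | 30 May 2018 |
| 11 mg once daily | 24 Feb 2016 | 14 Dec 2017 | 12 Dec 2019 |
| 10 mg twice daily | not approved | not approved | 30 May 2018 |
| 22 mg once daily | not approved | not approved | 12 Dec 2019 |

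A prescription written for RA or PsA would, if on-label, be 5 mg twice daily or 11 mg once daily. From 30 May 2018 to 12 December 2019 (561 days, about 18 months), 11 mg was on-label for RA and PsA but not for UC. That is 561/2,588 = 22% of the calendar window from 30 May 2018 to 30 June 2025. The percentage describes calendar time, not patients. Over-representation in the lower-dose strata is therefore likely, and the 11 mg stratum is the most exposed.

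**Step 3: what would it do to a dose contrast?** The protocol has no sample size, event target or planned rate ratio, so there is no figure to reproduce. The following is an illustration only, and every input is an assumption:

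- T = true high/low rate ratio among patients with UC only; here 1.5
- R = event rate in patients who also have RA or PsA, relative to UC only at the same dose; 0.7 to 2.0
- fl, fh = their share of person-time in the lower-dose and higher-dose strata; fl from 5% to 40%, fh = 0

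Seen ratio = T × [1 + fh(R − 1)] / [1 + fl(R − 1)]

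| R | fl = 5% | 10% | 20% | 40% |
|---|---|---|---|---|
| 0.7 | 1.52 | 1.55 | 1.60 | 1.70 |
| 1.0 | 1.50 | 1.50 | 1.50 | 1.50 |
| 1.5 | 1.46 | 1.43 | 1.36 | 1.25 |
| 2.0 | 1.43 | 1.36 | 1.25 | 1.07 |

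For example, with fl = 10% and R = 2.0, 1.5 / (1 + 0.10 × 1.0) = 1.36. If the higher-dose strata also hold 2% such patients, the shift is a little smaller: 1.5 × 1.02 / 1.10 = 1.39.

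**Step 4: when would the gradient vanish?** With fh = 0, the seen ratio reaches 1 when fl = (T − 1)/(R − 1). For T = 1.5 and R = 2.0 this is 0.5/1.0 = 50% of the lower-dose person-time.

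**The case against.** A reader might infer that patients with both conditions can be given only the lower regimens, so that they collect in those strata and hide a dose-related safety signal. The documents do not support this. The restriction in Section 7 belongs to the RA and PsA indications, and everyone in Cohort 1 also has UC codes. Section 9.3.2 counts as on-label "After May 2018, a prescription of tofacitinib 10 mg twice daily occurring only after a diagnosis of UC (as defined above", with no exception for coexisting arthritis, and treats 22 mg once daily the same way after December 2019. No dose distribution, share or event rate is given for these patients. If their rate is lower, the bias runs the other way.

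There are further points on the other side. The study is descriptive: "No a priori hypotheses are specified", and no rate ratio between doses is planned. A UC patient who also has RA belongs to the target population. The specialist-code rule and the bar on potent immunosuppressants will remove some patients treated for arthritis, and 9.9 already admits code misclassification. The subgroup and comorbidity lists are open, so the SAP could add the split.

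These points limit the size of the problem and rule out calling it a demonstrated masking effect. They do not remove it. The cohort definition is fixed in the protocol, rates by dose are set against each other there, and nothing in the text commits to showing how many patients in each stratum have RA or PsA.

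Nor does the point extend to Cohorts 2 and 3. They have no tofacitinib dose strata, so confounding of a dose contrast cannot arise there.

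**Conclusion.** The point holds as possible confounding by indication in the Cohort 1 dose strata. That patients with RA or PsA can enter is certain from the text. That they are over-represented at 5 mg and especially 11 mg is a reasonable inference from the approved regimens and dates, but no count supports it. The effect on the rates is unknown in both size and direction.

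At shares of 5% to 10% of the lower-dose stratum, with 1.5 to 2 times the event rate and none in the higher-dose strata, a true ratio of 1.5 appears as 1.36 to 1.46, a modest shift. With equal rates there is none. With R = 0.7 over the same shares the ratio appears as 1.52 to 1.55. Large distortion needs shares well above 10%, and complete masking needs half the stratum at double the rate. This is a cheap improvement worth making; it does not show that the planned rates are wrong.

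**What to change.** In 9.7.2 and 9.7.4:

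- Flag Cohort 1 patients who meet the 9.3.2 definition of RA or PsA before the index date.
- Report their number in each of the four dose strata.
- Add a prespecified sensitivity analysis that repeats the overall and dose-stratified Cohort 1 rates without them, to be read next to the main analysis whenever dose is discussed.

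Keep the main analysis as it is. The restricted version should not become the only basis for statements about dose. It drops genuine UC patients, including any on the higher regimens, and an RA or PsA code does not prove that the prescription was for arthritis.

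The cost is one flag from definitions that the utilization part already needs, plus one extra set of tables. The restricted version has a somewhat smaller lower-dose stratum and wider intervals. Under 9.7.3 the interim reports give overall results only, so dose-stratified rates first appear in the final report. The addition can be fixed in writing before those rates are produced.
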